4.4. CCI	
4.5. Other Safety Analyses	39
4.5.1. Extent of Exposure	40
4.5.2. Adverse Events.....	40
4.5.3. Additional Safety Assessments.....	40
4.6. Other Analyses	42
4.6.1. Subgroup analyses	42
4.6.2. Sensitivity Analyses	43
4.7. Interim Analyses	44
4.8. Changes to Protocol Defined Analyses	45
5. SAMPLE SIZE DETERMINATION	45
6. SUPPORTING DOCUMENTATION	45
6.1. Appendix 1 Study Population Analyses.....	45
6.1.1. Subject Disposition	45
6.1.2. Demographic and Baseline Characteristics.....	46
6.1.3. Protocol Deviations	46
6.1.4. Prior and Concomitant Medications and Vaccinations	47
6.1.5. Study Intervention Compliance	47
6.1.6. Additional Analyses Due to the COVID-19 Pandemic	47
6.2. Appendix 2 Data Derivations Rule	47

CONFIDENTIAL

6.2.1.	Baseline Immunogenicity	48
6.2.2.	Assessment Window	48
6.2.3.	Multiple measurements at One Analysis Time Point	48
6.2.4.	Attributing events to vaccine doses.....	49
6.2.5.	Handling of Missing Data	49
6.2.6.	Data Derivations	51
6.2.7.	Display of decimals.....	54
7.	REFERENCES.....	55

Version history

SAP Version	Approval Date	Protocol Version (Date) on which SAP is Based	Change	Rationale
1.0	12 Mar 2024	Amendment 1 Final: 15 June 2020	Not Applicable	Original version
2.0	12 Mar 2024	Amendment 1 Final: 15 June 2020		
			
Section 1.2:
 
 Added immunogenicity summaries where Visit 1, Visit 2, and Visit 3 in the LTFU phase of ZOSTER-073 will also be presented as Day 1, Month 12, and Month 24, 	
 In accordance to the primary endpoint timepoints for public disclosure
			
Section 3.1:
 
 Added PPS(LTFU) as a population that elimination code 2060 is applicable to and clarified the type of elimination is Visit(s) only, as applicable 	
 Concomitant infections could occur in the LTFU phase which could impact immunogenicity assessments at a particular visit or visits
			
Section 4.2:
 
 Clarified the immunogenicity 	
 Clarification that

SAP Version	Approval Date	Protocol Version (Date) on which SAP is Based	Change	Rationale
			summaries of seropositivity rates, GMCs, and MGI of anti-gE antibody in the LTFU phase will not be provided by age and immunosuppressive therapy	summaries will no longer be provided by subgroup
			
Section 4.2.2.1:
 
 Added reference point for MGI Added summaries of GMCs, MGI, and seropositivity in LTFU phase presented as Day 1, Month 12, and Month 24, in 	
 To clarify MGI reference point To present as Day 1, Month 12, and Month 24 for protocol primary endpoint timepoints public disclosure
			
Section 4.2.2.2 and Section 4.3.1.2.3:
 
 Added Boxplots of anti-gE antibody concentrations will be displayed by visit. 	
 Visual representation of summary statistics
			
Section 4.3.2.1:
 
 Added Visit 3 Month 23 to pre- 	
 Clarification of visit

SAP Version	Approval Date	Protocol Version (Date) on which SAP is Based	Change	Rationale
			
revaccination timepoints
 
 Added summaries of suspected or biopsy proven allograft rejections and HZ cases from ZOSTER-041 last visit to ZOSTER-073 Day 1 Added summary of HZ cases from ZOSTER-073 Day 1 to Visit 3 Month 24 	
associated with pre-revaccination
 
 To ensure biopsy rejections are summarized across all phases of study To ensure HZ cases are summarized across all phases of study
			
Section 4.3.2.2:
 
 Added summaries of non-serious unsolicited AEs, non-serious causally related unsolicited AEs. Added summary of biopsy rejections from Dose 1 up to 12 months post last revaccination. Added summary of causally related 	
 To separate non-serious from combined non-serious and serious unsolicited AE summaries To cover an additional portion of the revaccination follow up phase. Summary is needed for

SAP Version	Approval Date	Protocol Version (Date) on which SAP is Based	Change	Rationale
			
fatal unsolicited AEs.
 
 Added definition of allograft dysfunction Removed number of doses followed by SAE summaries 	
public disclosure.
 
 To clarify which creatinine values constitute allograft dysfunction SAEs are captured throughout the study not just within 30 days so cannot attribute to a dose
			
Section 4.4.2:
 
 CCI [REDACTED] [REDACTED] [REDACTED] [REDACTED] [REDACTED] 	
 CCI [REDACTED] [REDACTED] [REDACTED] [REDACTED]
			
Section 4.6.1:
 
 Changed from 2 to 3 immunosuppressive therapy subgroups. Clarified immunogenicity 	
 Single classes to be separate from 2 class combinations.

SAP Version	Approval Date	Protocol Version (Date) on which SAP is Based	Change	Rationale
			summaries will not be provided by subgroups	
			
Section 4.5.2.2:
 
 Removed COVID severity and outcome, AEs potentially indicating COVID, COVID symptoms, and COVID additional assessment summaries and listings . 	
 Company guidance and requirements for COVID summaries changed so removed to keep in line with all other studies in pipeline.
			
Section 4.5.3.1:
 
 Removed text about biopsy rejection. Added text about allograft dysfunction summaries and time points 	
 Text was already described in Section 4.3.2.2, removed to avoid duplication. To clarify how the creatinine measurements will be displayed for allograft dysfunction endpoints.

SAP Version	Approval Date	Protocol Version (Date) on which SAP is Based	Change	Rationale
			
Section 4.5.3.4:
 
 Added the timepoints in which the number of subjects with HZ episodes would be tabulated. 	
 To clarify multiple summaries will be provided based on study phase.
			
Section 6.1.1
 
 Updates text to state enrollment by country will be presented as part of demographic summaries. 	
 Moved country to demography summaries to reduce table counts
			
Section 6.1.2:
 
 Removed text about visit specific medical history listings 	
 To clarify only one medical history listing will be provided
			
Section 6.1.4:
 
 Added the following indications to the medical history summaries: anti-viral treatment for HZ, pain rescue medication to control HZ pain, 	
 To include all medical indications on the CRF for concomitant medications.

SAP Version	Approval Date	Protocol Version (Date) on which SAP is Based	Change	Rationale
			
and other therapy for HZ.
 
 Moved sentence stating the duration of therapeutic immunosuppressive therapy will be displayed in the listing of concomitant medications from 6.5.3.1 	
 Applied to concomitant medications listing not other safety measurements.
			
Section 6.1.3:
 
 Added text stating not revaccinated subjects will be summarized with the protocol deviations resulting in exclusion. 	
 While not a protocol deviation per se, these subjects are eliminated from exposed set and PPS for revaccination active and follow-up phases.
			
Section 6.1.4:
 
 Added text that concomitant medication indications of Pain for HZ and other HZ meds will be displayed 	
 Clarified all indications will be displayed

SAP Version	Approval Date	Protocol Version (Date) on which SAP is Based	Change	Rationale
			
Section 6.2.3:
 
Added text defining baseline and post baseline definitions in regards to rejection episodes, post-revaccination, and HZ episodes.	
To clarify how to handle multiple measurements for each type of summary.

1. INTRODUCTION

The purpose of this statistical analysis plan (SAP) is to describe the planned analyses to be included in the clinical study report (CSR) for Study 212340 (ZOSTER-073 EXT:041 Y4-10).

Details of the planned interim and final analyses are provided.

1.1. Objectives and Endpoints

Objectives	Endpoints
Primary	
LTFU phase - Immunogenicity assessment 
 To evaluate persistence of humoral immunity after primary vaccination course. 	In all subjects: 
 Anti-gE antibody concentrations as determined by ELISA at Day 1, Month 12, and Month 24.
Revaccination active phase - Immunogenicity assessment 
 To evaluate humoral immunity of HZ/su vaccine post-revaccination Doses 1 & 2. 	In all subjects: 
 Anti-gE antibody concentrations as determined by ELISA at pre-revaccination (Month 24) and at 1-month post-revaccination Dose 1 (Month 25) and Dose 2 (Month 26).
Secondary	
LTFU phase - Immunogenicity assessment 
 To evaluate persistence of cellular immunity after primary vaccination course. 	In CMI sub-cohort: 
 Frequencies of gE-specific CD4+ T-cells expressing two or more markers such as IFN-γ, IL-2, TNF-α, CD40L as determined by ICS at Day 1, Month 12, and Month 24.
LTFU phase - safety assessment 
 To evaluate safety of HZ/su vaccine from the study ZOSTER-041 last visit to study ZOSTER-073 Visit 3. 	In all subjects: 
 Related-SAEs 
 Occurrence of SAEs related to primary vaccination as assessed by the investigator from the study ZOSTER-041 last visit (Month 13) to study ZOSTER-073 Visit 3 (Month 24). HZ episodes 
 Occurrence of suspected or confirmed HZ cases from the study ZOSTER-041 last visit (Month 13) to study ZOSTER-073 Visit 1 (Day 1). Occurrence of confirmed HZ cases from Day 1 through Month 24. AESIs 
 Occurrence of suspected or biopsy-proven allograft rejections from the study ZOSTER-041 last visit (Month 13) to study ZOSTER-073 Visit 1 (Day 1). Occurrence of biopsy-proven allograft rejections from Day 1 through Month 24.

Objectives	Endpoints
	
 Allograft function for episode(s) of allograft rejection. 
 Occurrence of allograft dysfunction through assessment of all clinically obtained serum creatinine measures from 2 months prior to an episode of biopsy-proven rejection and up to 2 months after rejection resolution and cessation of therapeutic immunosuppressive therapy for the time period from study ZOSTER-041 last visit (Month 13) to study ZOSTER-073 Visit 3 (Month 24). Allograft function for episode(s) of HZ 
 Occurrence of allograft dysfunction through assessment of all clinically obtained serum creatinine measures from 2 months prior to an episode of HZ and up to 2 months after HZ rash resolution for the time period from study ZOSTER-041 last visit (Month 13) to study ZOSTER-073 Visit 3 (Month 24).
Revaccination active phase - Immunogenicity assessment 
 To evaluate cell-mediated immunity post- revaccination Doses 1 & 2. 	
In revaccinated subjects in CMI sub-cohort:
 
 Frequencies of gE-specific CD4+ T-cells expressing two or more markers such as IFN-γ, IL-2, TNF-α, CD40L as determined by ICS at pre-vaccination (Month 24) and at 1-month post-revaccination Dose 1 (Month 25) and Dose 2 (Month 26).
Revaccination follow-up phase – Immunogenicity assessment 
 To evaluate persistence of humoral and cell-mediated immune responses post-revaccination Dose 2. 	
In all revaccinated subjects:
 
 Anti-gE antibody concentrations as determined by ELISA at 12 months and 24 months post-revaccination Dose 2. 
In revaccinated subjects in CMI sub-cohort:
 
 Frequencies of gE-specific CD4+ T- cells expressing two or more markers such as IFN-γ, IL-2, TNF-α, CD40L as determined by ICS at 12 months and 24 months post-revaccination Dose 2 in a CMI sub-cohort of subjects.
Revaccination active and follow-up phases - Safety assessment 
 To evaluate reactogenicity and safety of the HZ/su vaccine after each revaccination. 	
In all revaccinated subjects:
 
 Solicited local and general AEs: 
 Occurrence, duration, and intensity of solicited local AEs within 7 days after each revaccination (i.e., the day of revaccination and 6 subsequent days); Occurrence, duration, and intensity of solicited general AEs within 7 days after each revaccination dose (i.e., the day of revaccination and 6 subsequent days) and causal relationship to revaccination by investigator assessment. Unsolicited AEs

Objectives	Endpoints
	
 – Occurrence, intensity of unsolicited AEs during 30 days after each revaccination (i.e., the day of revaccination and 29 subsequent days) and causal relationship to revaccination by investigator assessment. • SAEs 
 – Occurrence of SAEs (including fatal SAEs) from Dose 1 of revaccination (Month 24) until 12 months post-last revaccination dose (Month 37). – Occurrence of related-SAEs (including related-fatal SAEs) as per investigator assessment from Dose 1 of revaccination (Month 24) up to study end (Month 49). • AESIs 
 – Occurrence of all biopsy-proven allograft rejections from Dose 1 of revaccination (Month 24) up to study end (Month 49) and causal relationship to revaccination by investigator assessment. – Occurrence of pIMDs from Dose 1 of revaccination (Month 24) up to 12 months post-last revaccination dose (Month 37) and causal relationship by investigator assessment. • HZ episodes 
 – Occurrence of confirmed HZ cases from Dose 1 of revaccination (Month 24) up to study end (Month 49). • Allograft function following revaccination 
 – Occurrence of allograft dysfunction through assessment of all clinically obtained serum creatinine measures from 3 months before the first revaccination dose until 3 months after the last revaccination dose. • Allograft function for episode(s) of allograft rejection 
 – Occurrence of allograft dysfunction through assessment of all clinically obtained serum creatinine measures from 2 months prior to an episode of biopsy-proven rejection and up to 2 months after rejection resolution and cessation of therapeutic or immunosuppressive therapy. • Allograft function for episode(s) of HZ 
 – Occurrence of allograft dysfunction through assessment of all clinically obtained serum creatinine measures from 2 months prior to an episode of HZ and up to 2 months after HZ resolution.

Objectives	Endpoints
CCI	Tertiary

CMI = Cell-Mediated Immunity; **CCI** = Enzyme Linked Immunosorbent Assay; **gE** = glycoprotein E; **ICs** = Intracellular Cytokine Staining; **IL-2** = Interleukin 2; **TNF α** = Tumor Necrosis Factor-alpha; **IFN γ** = Interferon-gamma; **AE** = Adverse Event; **SAE** = Serious Adverse Event; **HZ** = Herpes Zoster; **AESI** = Adverse Event of Special Interest; **pIMDs** = potential Immune-Mediated Diseases.

*To be performed by a central laboratory if deemed necessary

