Secondary	
 Percentage of subjects with at least one local AE (solicited and unsolicited), with at least one general AE (solicited and unsolicited), and with any AEs during the solicited 7-day follow-up period will be tabulated with exact 95% CI after each revaccination dose and overall. The same computations will be done for Grade 3 AEs. Percentage of subjects reporting each individual solicited local AE (any grade and Grade 3) and solicited general AE (any grade, Grade 3, any related and Grade 3 related) during the 7-day follow-up period (i.e., on the day of revaccination and 6 subsequent days) will be tabulated after each revaccination dose and overall. Duration of solicited local and general AEs within 7 days and entire duration will be tabulated overall. Percentage of subjects with any unsolicited AEs during the 30-day follow-up period (i.e., on the day of revaccination and 29 subsequent days) with its exact 95% CI will be tabulated by Medical Dictionary for Regulatory Activities (MedDRA) preferred term. Similar tabulation will be done for Grade 3 unsolicited AEs, for any causally related unsolicited AEs, for Grade 3 causally related unsolicited AEs, for Grade 3 non-serious unsolicited AEs, for Grade 3 causally related non-serious unsolicited AEs and for unsolicited AEs resulting in a medically attended visit. Percentage of subjects with at least one report of SAE classified by the MedDRA SOC and PTs and reported from revaccination Dose 1 up to 30 days and 12 months post- last revaccination dose will be tabulated with exact 95% CI. SAEs will be also described in detail. Percentage of subjects with at least one report of causally related-SAE classified by the MedDRA SOC and Preferred Terms and reported from revaccination Dose 1 up to 30 days and 12 months post-last revaccination dose, and up to study end (Month 49) will be tabulated with exact 95% CI. Related-SAE will be also described in detail. Percentage of subjects with at least one pIMD classified by the MedDRA SOC and Preferred Terms and percentage of subjects with at least one pIMD with causal relationship, reported from Dose 1 up to 30 days and 12 months post- last revaccination dose will be tabulated with exact 95% CI. Percentage of subjects with at least one biopsy-proven allograft rejection and causal relationship reported from Dose 1 up to study end (Month 49) will be tabulated with exact 95% CI. Percentage of subjects reporting unsolicited AEs resulting in a medically attended visit from Dose 1 up to 30 days post-last revaccination dose will also be tabulated with exact 95% CI. Fatal SAEs will be described by onset date of SAE and date of death SAEs (including fatal SAEs), pIMDs and withdrawal due to AE(s) will be described in detail. Listing of withdrawals due to AE and SAEs will be provided Listing of subjects with confirmed HZ episode will be provided. Listing of subjects with biopsy-proven allograft rejection will be provided.

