4.3.2.2. Revaccination phase

The results for the analysis of safety in the revaccination phase will be tabulated as follows:

- Number and percentage of subjects with at least one local AE (solicited and unsolicited), with at least one general AE (solicited and unsolicited), and with any AEs during the solicited 7-day follow-up period will be tabulated with exact 95% CI after each revaccination dose and overall. The same computations will be done for Grade 3 AEs and medically attended AEs. Number and percentage of subjects reporting each individual solicited local AE (any grade and Grade 3) and solicited general AE (any grade, Grade 3, any related and Grade 3 related) during the 7-day follow-up period (i.e., on the day of

[figure not shown]
revaccination and 6 subsequent days) will be tabulated after each revaccination dose and overall.

- Duration of solicited local and solicited general AEs within 7 days and entire duration (lasting longer than 7 days) will be tabulated descriptively overall.
- Number and percentage of subjects with any unsolicited AEs during the 30-day follow-up period (i.e., on the day of revaccination and 29 subsequent days) with its exact 95% CI will be tabulated by MedDRA Primary SOC and PT. Similar tabulations will be done for Grade 3 unsolicited AEs, for any causally related unsolicited AEs, for Grade 3 causally related unsolicited AEs, for Grade 3 non-serious unsolicited AEs, for Grade 3 causally related non-serious unsolicited AEs, non-serious unsolicited AEs, non-serious causally related unsolicited AEs, and for unsolicited AEs resulting in a medically attended visit.
 - The number and percentage doses followed by unsolicited AEs during the 30-day follow-up period with its exact 95% CI will also be tabulated.
- Number and percentage of subjects with at least one report of SAE classified by MedDRA Primary SOC and PT and reported from revaccination Dose 1 up to 30 days post-last revaccination dose, from revaccination Dose 1 up to 12 months post- last revaccination dose, and from revaccination Dose 1 up to study end will be tabulated with exact 95% CI.
- Number and percentage of subjects with at least one report of causally related-SAE classified by MedDRA Primary SOC and PT and reported from revaccination Dose 1 up to 30 days post-last revaccination dose, from revaccination Dose 1 up to 12 months post-last revaccination dose, and from revaccination Dose 1 up to study end will be tabulated with exact 95% CI.

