6.2.4. Attributing events to vaccine doses

The dose relative to an event is the most recent vaccine dose given to a subject prior to the start of a given event. For example, if the start date of an adverse event is between Dose 1 and Dose 2, the relative dose will be Dose 1.

If an event starts on the same day as a study dose, the relative dose will be derived from the additional information provided in the case report form (CRF) using the contents of the flag indicating if the event occurred before or after study dose. If 'after vaccination' is selected, the relative dose for the event will be the one administered on the start day of the event. If 'vaccination' is selected, the relative dose for the event will be the dose prior to this one.

The number of doses is the number of times the vaccine was administered to a subject

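### Solicited-AE duration and 30-day unsolicited AEs are endpoints after each revaccination, but no by-dose table is specified for either

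*SAP*

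**What the plan says.** SAP 1.1 states the objective for the revaccination phases per dose: "To evaluate reactogenicity and safety of the HZ/su vaccine after each revaccination". Two endpoints under it carry the same wording:

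- Solicited local AEs: "Occurrence, duration, and intensity of solicited local AEs within 7 days after each revaccination". Solicited general AEs are worded alike, with causality added.
- Unsolicited AEs: "Occurrence, intensity of unsolicited AEs during 30 days after each revaccination (i.e., the day of revaccination and 29 subsequent days", with the investigator's causality assessment.

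The tables planned in SAP 4.3.2.2 are:

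- **Duration:** "Duration of solicited local and solicited general AEs within 7 days and entire duration (lasting longer than 7 days) will be tabulated descriptively overall". Protocol 10.3.4 agrees: "Duration of solicited local and general AEs within 7 days and entire duration will be tabulated overall".
- **30-day unsolicited AEs:** "Number and percentage of subjects with any unsolicited AEs during the 30-day follow-up period", by SOC and PT, repeated for Grade 3, causally related, non-serious and medically attended events. Protocol 10.3.4 has the subject-level table by preferred term.
- **Dose-level row, SAP only:** "The number and percentage doses followed by unsolicited AEs during the 30-day follow-up period with its exact 95% CI will also be tabulated".

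Other tables in the same SAP section are explicitly split by dose. These are subjects with any local, general or any AE in the 7-day window (solicited and unsolicited together, repeated for Grade 3 and medically attended events), and each individual solicited AE by grade, with relatedness for general AEs.

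**The concern.** Two endpoints are defined after each dose, and the tables as specified do not report them that way. The study gives two revaccination doses because the sponsor thought one might not be enough in this population (protocol sections 1 and 3.1), and SAP 4.2.2.2 shows humoral immunogenicity separately after Dose 1 and after Dose 2. A reader would expect the matching safety profile at the same two points. The analyses are purely descriptive (SAP 2.1), so the tables are the result, and no later model or test would recover the split.

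Duration matters most. Under SAP 6.2.5.4, a solicited reaction that continues past its observation period does not enter the unsolicited AE summaries. The duration table is then the only specified summary that shows a prolonged reaction, and it is not split by dose. If reactions lasted longer after Dose 2, no planned by-dose table would show it.

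**Working it through.** **Plan figures.** The plan states no AE rate, no expected duration and no number revaccinated, so there is no figure on this point to reproduce. The relevant size is the 68 subjects enrolled (SAP 1.2, Table 1), an upper bound on the number revaccinated.

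**Step 1: what is readable by dose under SAP 4.3.2.2**

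| Item | By dose? |
|---|---|
| Any, local or general AE in days 0-6, solicited and unsolicited combined; also Grade 3 and medically attended | Yes |
| Each solicited AE: any grade and Grade 3; relatedness for general AEs | Yes |
| Duration of solicited AEs | No, overall only |
| Unsolicited AEs alone: days 0-29, causality, SOC/PT | Not specified |

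Day 0 is the day of revaccination. The first row does not close the gap in the last. It merges unsolicited with solicited AEs, so a subject with any solicited reaction is already counted in the any-AE line. It stops at day 6, leaving days 7-29, and it has no causality version.

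**Step 2: is the missing split only shorthand?** The SAP states a dose split where it wants one: in the two 7-day tables above, for concomitant medication over the 30-day period (6.1.4), and for completeness of solicited-AE information (6.1.5). Read literally, 30-day medication use is shown by dose and 30-day unsolicited AEs are not.

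**Step 3: what the pooled figures can show.** Let p1 and p2 be the proportions with an unsolicited AE after Dose 1 and Dose 2, with every subject receiving both doses.

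- Percentage of doses = (p1 + p2) / 2.
- Percentage of subjects, if the two periods are independent = 1 - (1 - p1)(1 - p2).

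Assumed rates:

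- p1 = 0.20, p2 = 0.35: doses (0.20 + 0.35)/2 = 27.5%; subjects 1 - 0.80 × 0.65 = 48.0%.
- p1 = p2 = 0.275: doses 27.5%; subjects 1 - 0.725² = 47.4%.

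A 15-point rise and no rise differ by 0.6 points at subject level, which is 0.0056 × 68 = 0.4 of a subject. Both formulas are also symmetric in p1 and p2, so a rise and an equal fall give identical output.

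**Step 4: the same with counts.** If all 68 received both doses, 14/68 after Dose 1 (20.6%, exact 95% CI 11.7-32.1) and 27/68 after Dose 2 (39.7%, 28.0-52.3) pool to 41/136 doses = 30.1% (22.6-38.6). The reverse order gives the same 41/136. By-dose columns would separate the two cases.

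**Step 5: duration.** Suppose means of 2 days after Dose 1 and 4 days after Dose 2. With equal numbers reporting, the pooled mean is (2 + 4)/2 = 3. With 10 and 20 reporting it is (10 × 2 + 20 × 4)/30 = 3.3. The SD and range in the default summary (SAP 4.1.1) may widen, but they do not say after which dose the long durations arose.

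**The case against.** The strongest reply is that most of the by-dose safety profile is already planned. A reader might infer that the safety cost of the second dose cannot be read at all, or that more frequent reactions after Dose 2 would be averaged away. The documents do not support either reading. Frequency and Grade 3 of solicited reactions, relatedness of general ones, and combined 7-day AEs including medically attended ones are all planned after each dose. This part of the reply stands and sets the limits of the point.

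Second, SAP 4.3.2.2 never says that 30-day unsolicited AEs will be pooled. The window is defined relative to a dose, SAP 4.7 includes these events up to 30 days after each dose in the interim analysis, and SAP 6.2.4 attributes events to doses. This stands in part: for unsolicited AEs, pooling is inferred from wording and silence. However, SAP 4.7 sets a data window and 6.2.4 a derivation rule; neither commits to a by-dose table. For duration, *overall* could mean only that there is no age split, but neighbouring bullets name both the per-dose and the overall display.

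Third, one might object that the subject-level figure mixes subjects with one 30-day window and subjects with two. The dose-level row largely answers this, since it counts a one-dose subject once.

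Fourth, by-dose columns would not isolate the effect of the second dose. There is no one-dose arm, and events after Dose 1 can bar a subject from Dose 2 (protocol 7.7), so Dose 2 recipients are selected. This is correct and limits interpretation, but it does not remove the mismatch between endpoint and table.

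**Conclusion.** The point holds in a limited form. Solicited duration is an endpoint after each revaccination, and both documents tabulate it only overall. Unsolicited AEs over 30 days are also an endpoint after each revaccination, and no by-dose table is specified for them on their own, which leaves days 7-29, causality and the SOC/PT breakdown without a dose split. The first part is explicit in the text; the second is read from the absence of wording that appears elsewhere in the same plan.

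The size cannot be taken from the documents. The illustration rests on assumed rates, on all subjects receiving both doses and, for the subject percentage, on independence between doses. It shows only that the pooled figures barely change (27.5% of doses in both cases, 48.0% against 47.4% of subjects) while the underlying difference between doses goes from 15 points to none. The point does not mean that the second dose's reactogenicity is hidden in general, and no data are lost: the split can be produced from what is collected. It should be corrected, but it does not threaten the primary analyses.

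**What to change.** In SAP 4.3.2.2, and in protocol 10.3.4 to match, extend two bullets so that results are shown after Dose 1, after Dose 2 and combined:

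- the duration of solicited local and general AEs;
- the 30-day unsolicited AE tables, at least for any, Grade 3, causally related and medically attended events.

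Use the subjects who received the dose in question as the denominator, with exact 95% CIs for the proportions. Assign events by the existing rule in SAP 6.2.4: "The dose relative to an event is the most recent vaccine dose given to a subject prior to the start of a given event". Add a footnote that Dose 2 recipients are a selected subset and that the columns are descriptive.

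The cost is some wording and extra table columns; diary cards are already issued at each revaccination visit. The drawback is sparse cells, with at most 68 subjects per column spread over SOC and PT. If that is judged unhelpful, the summary row for each category could be given by dose and the SOC/PT detail kept combined, with that choice stated.
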